## 2. LAY SUMMARY

The NHS faces an unprecedented demand for services. Contributing to this increasing demand is a population who are living longer but not necessarily in good health. There is a rise in patients with long-term conditions requiring regular care from the NHS. As part of the response to this, research is aimed at investigating possibilities for system-wide transformation. The research will focus on testing the theory that information about patient behaviour, conditions and events can be gleaned from wearables, monitors and other smart technologies. This information could enable a better understanding of drivers or triggers for the demand of services and therefore inform strategic health commissioning.

If information about patient behaviour, conditions and events, captured from wearables, monitors and other smart technologies can predict demand for services, then, providing these technologies to patients and using the data generated will enable providers to pre-empt and redirect demand or design new services. This hypothesis will be tested in a PoC trial.

## 3. SYNOPSIS

Clinical Research Protocol L2S2 ltd Page 6 of 38

Study title	Service demand pred	iction based on information from o	connected devices							
Internal ref. no. / short title	Service demand pred	iction based on information from o	connected devices							
Study registration	IRAS Project ID 27614	9 17-11-2019								
Sponsor	[name]	Epping,								
Funder	NHS England, [name].									
Study Design	Clinical investigation	or other study of a medical device								
Study Participants	Patients older than 65 years AND more than 2 comorbid conditions AND / OR more than one requirements for unscheduled urgent care in previous year AND / OR medium or high frailty score									
Sample Size	Phase 1: 100; Phase 2	:: 500								
Planned Study Period		dy period: 11 months rticipation period 24 weeks								
Planned Recruitment period	Phase 1: April/May 2020 Phase 2: July/August 2020									
	Objectives	Outcome Measures	Timepoint(s)							
Primary	To test the hypothesis: If information about patient behaviour, conditions and events, captured from wearables, monitors and other smart technologies	Phase 1: 100 patients:  Optimised models generate dynamic personalised monitoring plan for each participant.  Phase 2: 500 patients:	July 2020							
	can predict demand for services, then, providing these technologies to patients and using the data generated will enable providers to preempt and redirect	Model linking health outcomes to NHS activity will be developed and tested.  Confidence of correlations between measured data and observed data from actual unscheduled care data during study period.	October 2020							

	demand or design new services.						
Secondary	Dropout Percentage: Number of readings taken by patients compared to their agreed plan.	Two percentages. Participants who can / want to receive automated compliance reminders. Participants who cannot / don't want to receive automated compliance reminders.	October 2020				
	Correlation between adherence to agreed plan and the participant's frailty score.	Correlation	October 2020				
	Number of visits required for each complication group by number of comorbid conditions to achieve best value	Table / charts / recommendations with confidence levels	October 2020				
	Correlation of each type of device with each complication group as a predictor of exacerbation (i.e. determine which device(s) are most useful).	Table of devices / correlations / confidence levels.	October 2020				
Intervention(s)	There are no clinical interventions in this study.						
Comparator	Comparison data wil study.	I be obtained from GP surgeries	participating in the				

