#### 5.2. Method

The study will use patient data held in care home and GP records to identify potential participants. Health professionals working for the participating care homes or GP surgeries will then use inclusion and exclusion criteria to select patients for invitation to join the study. In the care home phase (Phase 1), the care home manager will sign and hand an invitation letter and Patient Information Leaflet to the potential participants whom they have identified and ask them to sign an attached form giving consent to be approached by the research team for informed consent. In Phase 2, the primary care phase, GP surgery staff will send the invitation letter and Patient Information Leaflet to potential participant and process the returned forms, booking informed consent appointments. The research team is seeking the support of the North Thames Clinical Research Network in parallel with the application to the HRA/REC; if successful, staff from the CRN will support the recruitment and consenting process in Phase 2 only.

The study cohort will be taken from those who have needed most urgent care and who have the largest number of comorbidities, as defined by the inclusion and exclusion criteria above.

**Phase 1** of the study will be conducted with up to 100 participants residing in care homes. Either Health Research Assistants employed by the research team or local care home employed professionals (the choice between these two to be at the care home's discretion) will use connected medical devices to collect data from the cohort at twice-weekly intervals for twelve weeks. In this phase **all devices will be used with all participants**.

NHS activity data will be obtained from the records held in GPs' clinical systems at the end of Phase 1 to enable models to be constructed that will test the study hypothesis and allow the mapping of chronic conditions to device types to be optimised. This will mean that in **Phase 2**, participants will only be asked to use devices that have been proved in **Phase 1** to be effective at collecting useful data relevant to their specific set of co-morbidities.

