## 7.1. Visit Plan

## **Phase One**

- 1. Meeting with the participant to explain the purpose and form of the study and gain consent, conducted by a member of the project team. Average meeting time 30 minutes.
- 2. Research team will talk to care home professionals to gain participant's medical history, current medication and urgent care attendance history from locally-held record.
- 3. Initial meeting between the research team Health Research Assistant (HRA) and participant (or care home employed professional and participant). The timetable for the study will be discussed and dates for routine visits will be agreed as far as is possible. The HCA will conduct risk assessments to ensure that the patient can be tested safely. The HCA will use medical devices appropriate to the participant's medical condition determined by the HCA and historical data if available. Average meeting time 30 minutes.
- 4. Follow up visits by the HCA twice weekly to take measurements from the participant using all devices. This is expected to last for approximately 12 weeks per participant, but will end when either the participant exacerbates, elects to drop out of the study or the study ends.

Clinical Research Protocol CONFIDENTIAL

L2S2 ltd Page 17 of 38

5. A final visit will be conducted at the end of the study to ensure patients understand their rights with respect to data processing and retention. Average meeting time 30 minutes.

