#### **Phase Two**

- Meeting with the participant to explain the purpose and form of the study and gain consent, conducted by an appropriately trained professional at the GP surgery. Average meeting time 30 minutes.
- 2. Research team will access the participant's record in the GP's clinical system to gain participant's medical history, current medication and urgent care attendance history.
- 3. Initial meeting between the Health Research Assistant (HRA) and participant in their place of residence. The timetable for the study will be discussed and dates for routine visits will be agreed as far as is possible. The HRA will conduct risk assessments to ensure that the patient can be tested safely. The HRA will allocate medical devices appropriate to their medical condition as determined by the HRA and historical data if available. They will then explain how to use them. Average meeting time 60 minutes.
- 4. If requested by the participant, follow up visits by the HRAs will be carried out at approximately one week intervals for the remainder of the study to collect data and confirm that the participant is coping with the technology and not suffering physical or mental adverse effects. At each visit the HRA will use appropriate connected medical devices assigned to the participant to monitor both the effectiveness of equipping community staff with technology and to collect data professionally to contrast with self-measurements later in the study. Average meeting time 20 minutes.
- 5. Participants will be expected to participate for 12 weeks.
- Visits from HRAs may be offered proactively to participants by phone if they appear to be
  experiencing problems with using the devices, e.g. failure to charge the devices, improper use and
  sporadic use.
- 7. A final visit will be conducted at the end of the study to recover the equipment and ensure patients understand their rights with respect to data processing and retention. Average meeting time 30 minutes.

Participants will be encouraged to collect their own estimations of their frailty and condition (NICE guideline 56) throughout the trial for correlation against the measured data. (Participants will be asked to record data about their mood and how well they are feeling.)

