#### 27. Appendix E COVID-19 Procedures

Specific COVID-19 procedures have been added to the monitoring app and the care home staff research assistant's SOP.

Phase 1 of the trial was suspended because of the onset of COVID-19 in the UK. It was clear in February 2020 that visiting care homes would be unsafe and the UK was put into lockdown by the government on 23 March to attempt to limit the spread of coronavirus.

It appears that the government will gradually lift lockdown rules from June 2020 but it will be necessary to continue shielding of vulnerable participants for the foreseeable future. The study cohort is focussed on the over 65s with multiple co-morbidities and this group will be particularly susceptible to harm by COVID-19. It would not be possible to visit care homes under the government guidelines that state that care homes should restrict all non-essential healthcare visits.

The trial protocol has been revised to avoid the need for physical contact with the care homes and participants.

The Reassure app used to collect data in this trial has been updated to include secure video conferencing and safety features that make it possible to conduct the trial remotely and yet still obtain reliable data. The app is already in use in NHS hospitals to allow remote monitoring of participants at home during COVID-19.

Before COVID-19 it was intended that staff in some care homes would collect the participant data. Now only care homes that will allow their staff to collect data will be included in the trial. It is proposed that the care home staff will receive training via the app video link to enable them to use the devices safely and achieve good data quality.

The video will not be used for or with participants, only for staff assistance and training.

Each time it is used, the opening screen of the app will assess whether the participant is displaying the symptoms of COVID-19 infection.

It does this by requiring the staff member to follow an on-screen protocol as follows:

- At the start of each shift the staff member shall record their own temperature and answer COVID symptoms questions. If COVID is suspected, the app will prevent further use by that staff member until a negative result from a formal COVID-19 test is entered or until seven days have passed from the last symptoms. If the staff member is not suspected of having COVID0-19 the app continues as before.

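### The stated 2020 calendar cannot deliver the sequential design: Phase 2 recruitment opens before Phase 1 can supply its device mapping, and late Phase 2 recruits finish after the October outcome timepoint

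*Protocol*

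**What the plan says.** Section 3 (Synopsis) plans recruitment for Phase 1 in April/May 2020 and "Phase 2: July/August 2020". The same table places the Phase 1 outcome in July 2020, and the Phase 2 primary outcome and all secondary outcomes in October 2020.

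On duration, section 5.2 has Phase 1 staff "collect data from the cohort at twice-weekly intervals for twelve weeks". The Phase One visit plan in section 7.1 agrees ("This is expected to last for approximately 12 weeks per participant"), with an earlier end on exacerbation, dropout or close of the study. For Phase Two, section 7.1 says "Participants will be expected to participate for 12 weeks".

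On sequence, section 5.2 takes NHS activity data from GP systems once Phase 1 is over and uses them to build the models that match conditions to devices. As a result, in Phase 2 "participants will only be asked to use devices that have been proved in" Phase 1. Section 7 repeats that Phase 2 devices are allocated from Phase 1 data. Phase 2 activity data are likewise taken at the end of Phase 2 (section 5.2).

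Section 12.2 schedules an interim report on the first 100 care-home patients for the middle of May 2020 and leaves the timing of Phase 2 to a joint decision of the company and the CCG. Section 10.13 ends the study when the final report is presented, in October/November 2020. Appendix E records that "Phase 1 of the trial was suspended because of the onset of COVID-19 in the UK". Appendix B dates version 2.2 to 11 June 2020.

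**The concern.** The design is sequential: Phase 1 measures everyone with every device and Phase 2 uses what was learned. That works only if Phase 1 follow-up, the GP extract and the modelling are finished before Phase 2 devices are issued. The dates do not allow this, even before the COVID-19 suspension is considered.

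The back end has the same problem. The outcome is a comparison of device readings with GP activity data extracted after follow-up, but part of the Phase 2 cohort will still be under follow-up when the Synopsis reads the outcomes. A team working to this calendar would have to improvise on which evidence allocates devices, how long late recruits are followed, or when the outcomes are read. Those choices should be fixed in advance.

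**Working it through.** **Inputs.** Recruitment windows, outcome months and 12-week durations as above. Assumptions: each window runs from the first to the last calendar day of the named months, 12 weeks = 84 days, and mid-May = 15 May.

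**Phase 1 on the stated dates** (start + 84 days)
- 1 April + 84 = 24 June 2020
- 31 May + 84 = 23 August 2020
- Finishing by 30 June requires a start by 7 April, so recruits on 54 of the 61 window days finish after June.
- Finishing by 31 July, the latest reading of the July timepoint, requires a start by 8 May. Recruits on 23 of the 61 days finish later.

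Phase 2 recruitment opens on 1 July. These dates allow nothing for GP extraction or modelling.

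**The mid-May interim report**
- 1 April to 15 May = 44 days, about 6.3 weeks, and only for someone enrolled on the first day.
- Twelve weeks of data by 15 May would need a start by 21 February, before the window opens.
- The Phase 1 window is still open until 31 May, and the report date had passed when version 2.2 was issued.

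**Phase 1 after the suspension.** The protocol gives no restart date. If no usable records predate the suspension and Phase 1 restarts on or after 11 June, the first full record exists no earlier than 11 June + 84 = 3 September, after the Phase 2 window has closed.

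**Phase 2 on the stated dates**
- 1 July + 84 = 23 September 2020
- 31 August + 84 = 23 November 2020; the final visit about a week later (section 10.9) falls near 30 November.
- 31 October − 84 days = 8 August. Recruits of 9 to 31 August, 23 of 62 window days (37%), finish after October.

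**If Phase 2 waits for all Phase 1 follow-up** (no time added for extraction or modelling)
- Synopsis dates: Phase 2 starts 23 August; its first participant finishes 15 November; with a 62-day window the last finishes about 15 January 2021.
- Start on 3 September: first finish 26 November, last about 26 January 2021.

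In both cases every Phase 2 participant passes October.

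**Illustration only: what a hard cut-off would cost.** The protocol sets none. With even recruitment over the 62 days and Phase 2 not waiting for Phase 1:

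| Assumed cut | Recruits truncated | Mean days lost | Person-time lost | Last recruit followed |
|---|---|---|---|---|
| 31 October | 23/62 = 37% | (1+…+23)/62 = 276/62 = 4.5 | 4.5/84 = 5% | 61 days |
| 1 October | 53/62 = 85% | (1+…+53)/62 = 1431/62 = 23.1 | 23.1/84 = 27% | 31 days |

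**The case against.** The strongest reply is that these are planning dates with safeguards. Section 12.2 makes the move to Phase 2 a joint decision after an interim report on device and condition groupings. Section 6 sets the evaluation at the end of the study, which section 10.13 places in October/November, so 23 November lies inside it. Phase 1 measurement can stop early on exacerbation. Consent and device issue are separate steps in the Phase Two visit plan.

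Part of this stands. Phase 2 can be postponed, so the protocol does not force devices to be issued without a mapping. But the decision is tied to a report dated before Phase 1 could produce one full record. Participants without an event still need the whole 12 weeks, and they supply the specificity data. Separating consent from device issue moves follow-up later and makes the October overrun worse. The October/November allowance is for presenting the final report, and a last finish on 23 November plus a final visit uses almost all of it.

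A reader might infer four stronger things that the document does not support:
- **That follow-up will be truncated by the percentages above.** No section imposes a cut-off; a late report is at least as natural a result.
- **That the episode projection in section 12.1 fails.** Its Stage II table accumulates 175, 337 and 488 episodes over three months. Losing all of month 3 still leaves 337, against 0.35 × 560 = 196 implied by the sensitivity row of the sample-size table at 35% incidence. On the protocol's own figures no shortfall is shown.
- **That the Synopsis's participation "period 24 weeks" is a further contradiction.** Section 5.2 lets Phase 1 participants continue into Phase 2, and 12 + 12 = 24.
- **That 3 September is a fact.** It depends on the restart assumption, and the document does not say whether anyone was enrolled before the suspension.

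**Conclusion.** The point holds as an inconsistency between the calendar and the design. On the stated dates Phase 1 finishes between 24 June and 23 August 2020, so Phase 2 recruitment opens up to about eight weeks (1 July to 23 August = 53 days) before the last Phase 1 data exist. Phase 2 recruits enrolled after 8 August, 23 of 62 window days, finish after October, and the last finishes on 23 November. If Phase 2 waits as section 5.2 requires, all of its participants finish after October.

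This rests on calendar-month windows and full 12-week follow-up; the 3 September date also needs the restart assumption. No effect on the required sample size or on the number of expected episodes has been shown. The correction should be made because the passages cannot all be followed and the order they break is central to the study. It does not make the study infeasible.

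**What to change.** Reconcile the Synopsis, sections 5.2, 7.1, 10.13 and 12.2, and Appendix E by replacing calendar dates with milestones:

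1. The section 12.2 decision and Phase 2 device allocation follow a locked Phase 1 device mapping, built after Phase 1 follow-up and the GP extract are complete. Remove the mid-May date.
2. The Phase 2 outcome timepoint is 12 weeks after the last Phase 2 enrolment, plus a stated allowance for GP data extraction. The end of study follows from that.
3. State the Phase 1 restart date, and whether any records from before the suspension will be used.

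If October 2020 is contractually fixed, keep it, but state the data cut-off, the reduced follow-up for late recruits and the expected episodes under that cut-off.

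The cost is an amendment of dates and a later report. On the Synopsis dates, with Phase 2 waiting for Phase 1, the last follow-up would end about 15 January 2021 before extraction and analysis. No extra participants or measurements are needed.

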## 4. ABBREVIATIONS

CI	Chief Investigator
CRF	Case Report Form
CTRG	Clinical Trials & Research Governance, University of Oxford

GCP	Good Clinical Practice
GP	General Practitioner
HRA	Health Research Authority
ICF	Informed Consent Form
NHS	National Health Service
RES	Research Ethics Service
PI	Principal Investigator
PIL	Participant/ Patient Information Leaflet
R&D	NHS Trust R&D Department
REC	Research Ethics Committee
SOP	Standard Operating Procedure

#### 5. BACKGROUND AND RATIONALE

The study will focus on elderly people living both independently and in care homes, who experience regular health events which lead to NHS activity. To reach a statistically significant number of data points, whilst keeping cost and duration down, the study will target high risk patients who either have a history of repeat hospitalisations or have complex co-morbidities which results in frequent GP consultations and A&E visits.

This study focuses on the elderly for hypothesis testing. Our population is aging rapidly, driving changes in health and care needs in society. Between 2006 and 2016, the number of people over 65 years rose by 21% (1.7 million), with the 85's rising by more than 31% in England [1]. These demographic changes have been seen to have a significant impact on primary care - between 2011 and 2014, the number of annual GP appointments per person grew by 15.4%, mostly driven by growth among people over 65 years (growth among people under 65% was only 4% and population growth was 2%) [1]. Delays in accessing primary care have serious consequences for time-sensitive conditions such as ambulatory care sensitive conditions (ACSCs). Delayed interventions may result in avoidable ambulance and emergency department use, necessitate more intensive therapy and hospitalisation, or lead to increased morbidity or mortality. Hospital admissions for elderly with ACSCs have risen rapidly over the last decade and are currently estimated to account for 20-30% of hospitalisations [2,3]. Those suffering from multiple chronic conditions are most vulnerable [4-6]. Hospital admissions can be particularly disruptive to the elderly, exposing them to hospital acquired infections, functional decline and increasing dependency. With patients over 65 years accounting for 80% of the emergency admissions who stay for more than 2 weeks, these risks are very severe [7,8].

Studies have previously demonstrated the ability of telemedicine to decrease use of emergency departments and hospitalisations among vulnerable populations such as children and the elderly [9-12]. However, existing tools and guidelines were developed for the identification and management of individual health issues, verticalising problems. Yet, a complex patient suffers from multi-morbidity and polypharmacy. Consequently, they are often treated via a conglomeration of juxtaposed guidelines, taking more than 10 drugs a day with no certainty of efficacy [13]. Hence, the current disease-focused approach has been repeatedly subjected to scrutiny, calling instead for a patient-centred approach focused on

personalised appropriateness and adherence [13,14]. The impact of a high-intensity telemonitoring model for holistic geriatric health (identification of acute disease & chronic exacerbations) implemented in senior communities has been documented by Shah et al [15,16]. Building upon this preliminary evidence, the study will conduct a structured evaluation of the ability of a holistic data collection process in the community to enable early detection of unplanned health needs in complex patients such as the elderly. Moreover, as evident from data submitted by the Authority, in West Essex, people over 65 constitute the majority of patients with complex healthcare needs and lead to the majority of expenditure on hospital admissions (Figure 2).

